Study Protocol

TITLE: Brain stimulation study of human visually-guided navigation using repetitive transcranial magnetic stimulation (rTMS)

NCT NUMBER: NCT04961645

Protocol Date: April 11, 2021

PROTOCOL TITLE: Brain stimulation study of human visually-guided navigation using repetitive transcranial magnetic stimulation (rTMS)

EXTERNAL (NON-EMORY) COLLABORATORS

None

PRINCIPAL INVESTIGATOR:

Name: [name]

Department: Department of Psychology

Telephone Number:

Email Address:

VERSION: 1.00 - 04/11/21

FUNDING SOURCE: NIH 5-R01-EY029724 - 03, Department

Page 1 of 17 IRB Form BIO 03152021

REVISION HISTORY

Revision #	Version Date	Summary of Changes

Table of Contents

1.	Study Summary	5
2.	Objectives	5
3.	Background	5
4.	Study Endpoints	5
5.	Study Intervention/Investigational Agent	6
6.	Procedures Involved	6
7.	Data Specimen Banking	7
8.	Sharing of Results with Participants	7
9.	Study Timelines	8
10.	Inclusion and Exclusion Criteria	8
11.	Vulnerable Populations	8
12.	Local Number of Participants	9
13.	Recruitment Methods	9
14.	Withdrawal of Participants	10
15.	Risk to Participants	
16.	Potential Benefits to Participants	10
17.	Compensation to Participants	
18.	Data Management and Confidentiality	10
19.	Provisions to Monitor the Data to Ensure the Safety of Participants	11
20.	Provisions to Protect the Privacy Interest of Participants	12
21.	Economic Burden to Participants	12
22.	Informed Consent	13
23.	Setting	15
24.	Resources Available	16
25.	Multi-Site Research When Emory is the Lead Site	16
26	References	17

1. Study Summary

Project Title	Brain stimulation and visually-guided navigation
Project Design	In this project, participants will volunteer, based on recruitment efforts such as the Psychology student database. There is no random assignment. The number of subjects for each experiment was determined using a power analysis. The intervention is transcranial magnetic stimulation (TMS).
Primary Objective	Testing the causal role of OPA using repetitive TMS (rTMS)
Secondary Objective(s)	None
Research Intervention(s)/Interactions	TMS
Study Population	Typical adults (18 years or above)
Sample Size	38
Study Duration for individual participants	2 visits – 90 minutes each
Study Specific Abbreviations/ Definitions	rTMS – repetitive transcranial magnetic stimulation OPA – Occipital Place Area fMRI – functional magnetic resonance imaging
Funding Source (if any)	NIH 5-R01-EY029724 - 03

2. Objectives

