i) If OPA is causally involved in visual scene navigation, then disruption of this region, using rTMS, will lead to a decrement in performance on the "visually-guided navigation task" (i.e., imagine you are walking through the room, and respond via button press whether they can leave through a door on the left, center, or right wall, as indicated by a continuous path on the floor), but not on the "scene categorization task" (i.e., imagine you are standing in the pictured room, and respond whether you are in a bedroom, kitchen, or living room) – the control *condition*.

Primary outcome measure: To determine baseline performance, we will also apply rTMS to a control site (i.e., the vertex – a bit of the brain at the very top of the head, not implicated in visually-guided navigation, and identified as the direct midpoint between the bridge of the nose and the inion, and between the participants' temples), and predict a decrement in performance on the visually-guided navigation task, only after rTMS is applied to OPA (but not vertex). There are no secondary outcome measures.

Experiments involving the simple behavioral task (i.e., actually walk around a small room and search for hidden objects).

ii) If OPA is causally involved in visually-guided navigation, then disruption of this region, using rTMS, will lead to a decrement in performance in navigating through the room to find a hidden object, but not in identifying what the object is (the control condition).

Primary outcome measure: As described just above, to determine baseline performance, we will also apply rTMS to the control vertex site, and predict a decrement in performance on the visually-guided navigation task, only after rTMS is applied to OPA (but not vertex). There are no secondary outcome measures.

5. Study Intervention/Investigational Agent

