We plan to enroll about 38 healthy adult participants (19 for each of the two proposed experiments). The number of participants was determined using a power analysis, with an effect size of $\eta_P{}^2 = 0.14$ (estimated from previous similar studies), an alpha level of 0.05, and power at two levels: 90% and 80%. Thus in each of the two proposed studies, we will test 19 participants (90% power), but could lose 4 participants to attrition and still have 80% power. Note in prior TMS studies, a similar number of participants were tested.

We will recruit an equal number of men and women, and all efforts will be made to recruit minorities. No exclusion of women and minorities is necessary for this study. Census estimates from 2010 for Atlanta, Georgia, were 43.1% white, 50.1% African American, 0.2% American

Page 9 of 17 Version: Version 1 04/11/21

Indian and Alaskan Native, 2.7% Asian, and <1% Native Hawaiian and other Pacific Islander; Hispanic or Latino were 5.3%. Using these census estimates, we will recruit minority participants to ensure that the subject sample represents the community. Recruitment of women and minorities will be assessed quarterly to ensure adequate representation. Participants will be recruited via the subject pool database maintained by the Emory University Psychology Department.

13. Recruitment Methods

Participants will be recruited via the subject pool database maintained by the Emory University Psychology Department. The database involves names and contact information of people who have agreed to participate in research for course credit (1 credit up to 60 minutes) or to be paid for their participation. However, the participants in this study will not receive credit, but rather will be paid \$20/hour in cash for the rTMS portion. For the fMRI portion, the participants will be paid \$25/hour. Additionally, participants may be recruited in the community and at Emory University by word of mouth. No flyers or printed advertisements will be used.

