To ensure that the participant does not have any metal in his or her body, the study team administers a screening form (attached) to the participant both during recruitment and before going into the scanner. Furthermore, to minimize any possible risk of a seizure during testing, the participant will certify that neither she, nor parents, brothers or sisters, or children have ever suffered an epileptic seizure. The participant will also certify that she has never suffered a known brain injury, and that she is not taking certain medications that may increase the risk of seizures or reduce the effects of rTMS. To ensure that the participant does not have any of the above contraindications, the study team administers another screening form (attached) to the participant both during recruitment and before study participation.

14. Withdrawal of Participants

Some people become nervous or claustrophobic (anxious or afraid of closed spaces) in the fMRI scanner. If this happens to the participant, they may ask to be withdrawn immediately. They may also experience a sense of dizziness in the magnet. Such dizziness is due to the strong magnetic field, and if it disturbs them, they may ask to be withdrawn.

The most common risk and discomfort of rTMS expected in this study is mild discomfort or tingling due to twitching of muscles in the head or face. If, at any time, the participant feels uncomfortable due to such twitching, he or she may indicate so verbally, and we will stop the experiment. In the studies cited above between 5-15% of participants experience discomfort, and withdraw from the study.

The study team has the right to end the subject's participation in this study for any of the following reasons: If it would be dangerous for the participant to continue, if the participant does

Page 10 of 17 Version: Version 1 04/11/21

not follow study procedures as directed by the study team, or if the sponsor decides to end the study.

The subject's participation is voluntary, and she has the right to refuse to be in this study. The participant can stop at anytime after giving her consent. The participant has the right to leave a study at any time without penalty. The participant may refuse to do any procedures the she does not feel comfortable with, or answer any questions that she does not wish to answer. If the participant choose to withdraw, she can request that her information not be used in the study.

15. Risk to Participants

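### The 90% and 80% power claimed in Section 12 do not follow from a partial eta-squared of 0.14; in its ordinary sense for a 1-df contrast, power is about 37-38% at n=19 and 29-31% at n=15

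*Combined protocol and SAP*

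**What the plan says.** Section 12 (Local Number of Participants) plans 38 adults, 19 in each of two experiments. The inputs to the power analysis are "with an effect size of $\eta_P{}^2 = 0.14$ (estimated from previous similar studies") and "an alpha level of 0.05, and power at two levels: 90% and 80"%. The conclusion is that "we will test 19 participants (90% power), but could lose 4 participants to attrition and still have 80% power". Nothing more is given: no test, no contrast, no sidedness, no number of repeated measures, no correlation between them, and no statement of what variance the 0.14 is relative to.

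Section 4 (Study Endpoints) sets out what is to be tested. Each experiment has one primary outcome and no secondary ones. The investigators "predict a decrement in performance on the visually-guided navigation task, only after rTMS is applied to OPA (but not vertex"), and expect no decrement on a control task. Vertex stimulation is the reference: "To determine baseline performance, we will also apply rTMS to a control site".

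Section 14 (Withdrawal of Participants) reports that in the cited studies "between 5-15% of participants experience discomfort, and withdraw from the study".

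**The concern.** A partial eta-squared of 0.14 corresponds to a standardised within-person difference (dz) of about 0.4. Nineteen participants would not ordinarily give 90% power for a difference of that size. Section 12 is the plan's only justification of sample size, and the Study Summary relies on it.

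If the stated power is wrong, each experiment could miss the effect it was designed for far more often than the 10% that the plan implies. This matters particularly here because the argument depends partly on finding no effect on the control task, and a null result is hard to interpret when the miss rate is unknown. The attrition allowance rests on the same calculation.

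**Working it through.** **Inputs.** From Section 12: partial eta-squared 0.14, alpha 0.05, n = 19, and n = 19 − 4 = 15. From Section 4: two sites (OPA, vertex) and two tasks, so both the site contrast and the site-by-task interaction have 1 df. My assumptions: the contrast is within participant (implied by vertex serving as baseline, but not stated) and the test is two-sided.

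**Effect size.** f² = 0.14 / (1 − 0.14) = 0.1628, so f = 0.403.

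**Step 1: reproducing 15 and 19.** In a repeated-measures formula that treats f as scaled to the individual measurements, the noncentrality is λ = f² · n · m / (1 − ρ), with m measures and correlation ρ. With m = 2 and ρ = 0.5 the multiplier is 2 / 0.5 = 4.

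- n = 19: λ = 0.1628 × 19 × 4 = 12.37; power from F(1, 18) is 91.4%.
- n = 15: λ = 0.1628 × 15 × 4 = 9.77; power from F(1, 14) is 82.8%.

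Under this setting 19 and 15 are the smallest n that reach 90% and 80%, so the plan's figures can be recovered, but only with inputs it does not state. Other 1-df settings give the same pair: m = 4 with ρ = 0, and m = 3 with ρ = 0.25. So do some settings with 2 or 3 df. For 1 df, exactly 15 and 19 result only when f² is multiplied by about 3.81 to 4.03. The tested contrast then has dz = √(4 × 0.1628) = 0.81 (range 0.79 to 0.81). At multiplier 4 its population partial eta-squared is 0.651 / 1.651 = 0.39, or about 0.41 on the sample scale.

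**Step 2: 0.14 in its ordinary sense.** If 0.14 is the contrast's own partial eta-squared, λ = f² · n, or f² · (n − 1) under the other common convention.

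| | n = 19 | n = 15 |
|---|---|---|
| λ | 2.93 to 3.09 | 2.28 to 2.44 |
| Power, two-sided | 36.7% to 38.4% | 29.1% to 30.8% |
| Power, one-sided | 50% to 52% | 42% to 44% |

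A simulation of 400,000 runs agrees with the upper two-sided figures (38.4% and 30.9%). Smallest n, two-sided: 51-52 for 80% and 67-68 for 90%. One-sided: 40-41 and 54-55.

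**Step 3: what 0.14 looks like in the data, on the same reading.** An observed partial eta-squared of exactly 0.14 with 19 participants gives F(1, 18) = 0.1628 × 18 = 2.93, p = 0.10. With 15 it gives F(1, 14) = 2.28, p = 0.15. The smallest significant observed value is F_crit / (F_crit + n − 1): 4.41 / 22.41 = 0.197 for n = 19, and 4.60 / 18.60 = 0.247 for n = 15.

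**Step 4: 0.14 on a total-variance scale, two measures.** Power then depends on the unstated correlation.

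| ρ | n = 19 | n = 15 |
|---|---|---|
| 0 | 65% | 54% |
| 0.25 | 78% | 66% |
| 0.5 | 91% | 83% |

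Reaching 90% at n = 19 needs ρ of about 0.47 or more.

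**Step 5: attrition.** Withdrawal of 5-15% of 19 is 0.95 to 2.85, or 1 to 3 people, leaving 16 to 18. Power at those numbers is 31-37% on the Step 2 reading, and 85-90% with the multiplier of 4 in Step 1.

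**The case against.** The strongest reply is that no arithmetic slip has been shown. One coherent formula returns both 15 and 19 exactly, which suggests a correct calculation with unreported settings. The 37-38% figure also needs assumptions that the plan does not state: 1 df, within participant, two-sided. Which figure applies depends on how the earlier studies defined 0.14, and those studies are not available here. The check in Step 3 adopts the disputed reading, so it illustrates that reading without helping to choose it. Finally, the allowance of 4 in 19 (21%) exceeds the withdrawal quoted in Section 14, and rewording Section 12 cannot raise power that is truly low.

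Much of this is fair. The 37-38% is conditional, the within-participant design is inferred, and the dropout sentence is not a separate defect.

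Three things remain. First, an ordinary partial eta-squared for a within-participant contrast already reflects the correlation between conditions, so applying a correlation again counts it twice. Second, every 1-df route to 15 and 19 powers the study for a contrast with partial eta-squared near 0.39, while the reader is told 0.14. Third, an ordinary reading with more degrees of freedom does not rescue the claim: taking λ = f² · n · df, power at n = 19 is about 56% with 2 df and 69% with 3 df.

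**Conclusion.** The concern holds. The stated power and attrition allowance do not follow from the stated effect size.

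If 0.14 is the partial eta-squared of a 1-df within-participant contrast tested two-sided, each experiment misses an effect of that size about 62-63% of the time (48-50% one-sided), against the stated 10%. If 0.14 is on a total-variance scale, 90% at n = 19 is attainable, but it rests on an unstated number of measures and correlation; with two measures, correlations from 0 to 0.5 give 65% to 91%.

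That the inputs are incomplete, and that the 1-df routes to 15 and 19 need a roughly fourfold inflation of f², is certain from the documents and the arithmetic. Which reading the authors intended cannot be settled from the documents. This must be corrected, because a reader of Section 12 would take 90% power for an effect of 0.14 at face value.

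**What to change.** Keep the sample size and rewrite the power paragraph in Section 12:

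- Name the powered contrast (OPA versus vertex on navigation, or site by task), whether it is within participant, and the sidedness.
- Define the 0.14: the contrast's own partial eta-squared, or an effect relative to total variance. Give the number of measures and any assumed correlation.
- State that 19 (15) participants give about 90% (80%) power for a within-participant dz of about 0.8, a partial eta-squared of roughly 0.38-0.41 for that contrast.
- If 0.14 is the contrast's own value, state that power is about 37-38% at n = 19 and 29-31% at n = 15. If it is a total-variance effect, say so and give power over a range of correlations, as in Step 4.
- Put the sentence about losing four participants on the same basis.

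The cost is rewording one section, with no added participants or procedures. The stated power becomes less favourable, or conditional on a named correlation. Rewording does not raise power: if the authors confirm the ordinary meaning of 0.14, they should acknowledge that each experiment has limited power for an effect of that size and that a null result would be weak evidence of no effect.

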During the second visit (the rTMS visit), participants will be seated comfortably in a chair and asked to complete either a simple computer-based task (e.g., imagine you are walking through the room, and respond via button press whether they can leave through a door on the left, center, or right wall, as indicated by a continuous path on the floor), or a simple behavioral task that will require them to actually walk around in a small room and search for hidden objects. Either during, or just before, each of these tasks, participants will receive rTMS. In rTMS, we place a small plastic coil next to the participant's head. The position of the coil will be guided by the fMRI study described just above, which was conducted on that participant in the prior visit. The coil will be placed over the relevant brain region using the Brainsight TMS-MRI co-registration system for visualizing the coil position with respect to the participant's individual fMRI scan. The coil will then generate a magnetic pulse, and stimulation will occur. During stimulation, the participants may feel a gentle flick, and hear an audible click. The pulse is not usually painful, but it can cause a twitch of the hand or face muscles. Even though hearing loss is a rare

Page 7 of 17 Version: Version 1 04/11/21

occurrence from rTMS, hearing protection (i.e., ear plugs) will be used during the TMS experiments.

Instead of having source records (i.e. surveys), we are only going to collect brain image data for the fMRI portion of the study and psychophysical data for the rTMS portion. No further data is collected after procedures are completed.

During the experiment, participants may withdraw at anytime. After the experiment, participants will remain under supervision for about 15 minutes, verbally confirm they feel safe to leave (after the 15 minutes), and then will be escorted to the exit. If participants do not feel safe to leave after the 15 minutes is up, they will be asked to stay until you do feel safe to leave. If further assistance is needed, [name] (M.D./Ph.D), the head of FERN, will be contacted to come to the testing room.

7. Data Specimen Banking

All participants will be given a non-identifying ID number. Hardcopy data will be kept in a locked filing cabinet in a secure office. Electronic data will be stored on a secure electronic hard drive. Electronic data will also be shared with Emory University and will be secured according to Emory IT policies.

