Finally, risk of seizures in healthy participants is very low, but not zero. Loo et al. (2008) provide a particularly useful and comprehensive review of all reported seizures in healthy participants that have occurred during TMS. In the first one, a participant experienced a seizure during TMS (Tharayil et al., 2005). This participant was taking chlorpromazine, and had some family history of epilepsy (a brother experienced a childhood seizure). In the second incident, an event resembling a seizure was reported during TMS stimulation (Nowak et al, 2006). However, that case is disputed and may instead have been an incidence of fainting, not a seizure (Epstein, 2007). In any case, no long-term effects were found in follow-up neurological exams or EEG. Given that these are the only two cases of seizures or possible seizures that have been reported from the thousands of participants (probably tens of thousands of participants by now) who have experienced TMS, the risk of such events from the stimulation in the proposed study would seem to be very small. That said, to minimize any possible risk of a seizure during testing, the participant will certify that neither she, nor parents, brothers or sisters, or children have ever suffered an epileptic seizure. The participant will also certify that she has never suffered a known brain injury, and that she is not taking certain medications that may increase the risk of seizures or reduce the effects of rTMS. To ensure that the participant does not have any of the above contraindications, the study team administers a screening form (attached) to the participant both during recruitment and before study participation. If, in the rare event, the participants experience a seizure, [name] (M.D./Ph.D.) will be contacted immediately to come to the testing room, and Emory EMS [contact]) will also be contacted immediately.

For the computer-based and behavioral tasks, the risks are minimal. The participant may become frustrated or tired. We will provide encouragement and rest-breaks as needed. During both tasks, a study assistant will be in the room with the participant the entire time.

16. Potential Benefits to Participants

There is no direct benefit to individual participants from taking part in this study.

Version: Version 1 04/11/21 Page 12 of 17

17. Compensation to Participants

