During the first visit (fMRI), participants will receive \$25/hour to compensate for their time and effort. During the second visit (rTMS), the participants will receive \$20/hour to compensate for their time and effort. If they do not finish the study, we will compensate them for the time they have completed.

18. Data Management and Confidentiality

All participants will be given a non-identifying ID number. Hardcopy data will be kept in a locked filing cabinet in a secure office. Electronic data will be stored on a secure electronic hard drive. Electronic data will also be shared with Emory University and will be secured according to Emory IT policies. Only study personnel who are involved in the project will be allowed access to these data, and are also responsible for receipt or transmission of these data. If a participant declines to participate in all portions of the study, the participant will not be assigned a study ID number and the study coordinators/data collects will refrain from collecting any data on the participant. If the participant agrees to participate in some portions of the study by not others, the participant will be assigned a study ID number and the study coordinators/data collectors will be instructed to collect data only on those aspects of the study to which the participant has agreed to participate. These procedures will help prevent unauthorized inclusion of the patient's data in the database.

19. Provisions to Monitor the Data to Ensure the Safety of Participants

All procedures in this research are minimal risk.

20. Provisions to Protect the Privacy Interest of Participants

Participants will only interact with at most two study personnel during their visits. No personal information, beyond the information from the screening forms discussed above (attached), will be asked.

21. Economic Burden to Participants

None.

22. Informed Consent

All participants will provide informed consent by reading and signing a consent form before any experiments begin. Informed consent will be sought and obtained from all participants at the [name] Lab in the Psychology Department, by members of the research team, who have all

Page 13 of 17 Version: Version 1 04/11/21

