Again, participants will be recruited via the subject pool database maintained by the Emory University Psychology Department. This database contains hundreds of prospective participants, enabling the recruitment of about 38 partcipants highly feasible. Likewise, the Psychology Department at Emory University has all of the facilities necessary to conduct and complete the research, as described just below. Finally, all persons assiting with the research will be adequately trained by the PI on the protocol, research procedures, and their duties.

Page 14 of 17 Version: Version 1 04/11/21

MRI and TMS: The Psychology Department has both its very own Siemens 3T magnetic resonance imaging (MRI) scanner, and TMS device, which are dedicated to research. In addition, we have a full-time director and technician for the center in which the scanner is housed, called the Facility for Education and Research in Neuroscience (FERN). Also in FERN is a mock scanner, which is especially important for training those participants who have never been in an MRI before.

Laboratory of the Principal Investigator: The [name] Lab in the Psychology Department is comprised of approximately 1000 square feet, and includes office space that can accommodate up to 6 full-time staff members (research assistants/ graduate students/postdocs), two behavioral testing rooms (one with a SR Research EyeLink 1000 Plus Eye Tracker), and a conference room. The laboratory is also equipped with a high-speed 6-core MacPro for imaging analysis, 4 MacAir laptops, a dedicated laptop for fMRI data acquisition, and three desktop work stations. All computers provide access to behavioral and neuroimaging analysis software, including Matlab, SPM 8/12, AFNI, FSL, SPSS, R and Python. Finally, my lab currently consists of four outstanding graduate students, who all have the full competency to collect and analyze fMRI, psychophysical, and TMS data.

25. Multi-Site Research When Emory is the Lead Site

This is not a multi-site study.

26. References

Bolognini, N. & Ro, T. (2010). Transcranial Magnetic Stimulation: Disrupting neural activity to alter and assess brain function. *Journal of Neuroscience*, *30*, 9647-9650.

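### Walking experiment: the protocol does not say how or by whom navigation performance is recorded, and nothing keeps that person unaware of the stimulated site

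*Combined protocol and SAP*

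**What the plan says.** Section 6 (Procedures Involved) describes the second experiment as a task that will "require them to actually walk around in a small room and search for hidden objects". rTMS may be given during the task or shortly before it. The same section says: "The coil will be placed over the relevant brain region using the Brainsight TMS-MRI co-registration system".

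Section 4 (Study Endpoints), hypothesis ii, predicts that disrupting OPA "will lead to a decrement in performance in navigating through the room to find a hidden object", while identification of the object is spared. Vertex stimulation supplies the baseline, and the decrement is expected after OPA stimulation only. No unit of performance (time, errors, path), instrument or recorder is named. Section 6 calls the rTMS-visit data psychophysical and does not say how they are captured.

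Section 15 (Risk to Participants) says of both tasks: "We will provide encouragement and rest-breaks as needed", and then that "a study assistant will be in the room with the participant the entire time". Section 20 (Privacy) says: "Participants will only interact with at most two study personnel during their visits". Section 24 (Resources Available) says "my lab currently consists of four outstanding graduate students", all described as competent to collect and analyse TMS data.

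No section mentions blinding, masking, scripted interaction, automated capture or independent scoring. Nothing suggests that such text was removed.

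**The concern.** The computer experiment is answered by button press, which leaves little room for an observer to affect the result. The walking search is more exposed. Someone has to start it, decide when it ends, and respond when a participant hesitates. If that person knows the site and the hypothesis, a small difference in prompting, encouragement or recording between OPA and vertex runs enters the primary contrast directly, and no later analysis could separate it from a true effect of stimulation.

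The walking task is the protocol's only test of physical navigation and carries one of its two primary outcomes. An unmasked, unrecorded session cannot be rescored later, so protection has to be arranged before data collection.

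**Working it through.** **1. The plan's own figure.** Section 12 gives partial eta squared 0.14, alpha 0.05, 19 participants per experiment for 90% power, and 15 remaining for 80%.

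- f² = 0.14/0.86 = 0.163, so f = 0.403.
- Assumptions not in the documents: two repeated measurements with correlation 0.5.
- Noncentrality = f² × n × 2/(1 − 0.5), with 1 and n − 1 degrees of freedom.
- Power is 0.897 at n=18 and 0.914 at n=19; it is 0.797 at n=14 and 0.828 at n=15.

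Both stated numbers reproduce, so the sample size is not in dispute. On this reading the planned effect is √(0.163 × 2/0.5) = 0.807 SD of the paired difference.

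**2. What the existing controls cover.**

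| Source of a spurious OPA decrement | Covered by vertex? | Covered by object identification? |
|---|---|---|
| Noise, discomfort or distraction common to both sites | Yes | Yes |
| General slowing or inattention after OPA stimulation | No | Yes |
| Observer who knows site and hypothesis and handles OPA navigation runs differently | No | No |

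The last row is not covered because the predicted pattern is itself specific to site and task.

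**3. What a bias of a given size would do.** The documents give no bias size. Assume no true effect, a two-sided paired test at 0.05 (neither the test nor its sidedness is stated), and a shift of b SD of the within-person difference. The test statistic is then noncentral t with 18 degrees of freedom and noncentrality b√19; the critical value is 2.101.

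| Assumed shift b | b√19 | Two-sided rejection | In predicted direction (nominal 2.5%) |
|---|---|---|---|
| 0 | 0 | 5.0% | 2.5% |
| 0.1 | 0.436 | 7.0% | 6.1% |
| 0.2 | 0.872 | 13.1% | 12.8% |
| 0.3 | 1.308 | 23.6% | 23.5% |

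The share of false positives in the predicted direction is about 87% at 0.1 SD (6.1/7.0), about 98% at 0.2 and over 99% at 0.3. With 15 participants the two-sided rates are 6.5%, 11.2% and 19.2%.

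For scale, 0.1, 0.2 and 0.3 SD are 12%, 25% and 37% of the 0.807 SD in step 1. A shift of 2.101/√19 = 0.48 SD would by itself put the expected difference at the significance threshold.

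The same formula applies if the primary test is the site-by-task interaction, with b expressed in SD of that within-person contrast. In that case only bias specific to OPA navigation runs contributes.

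**The case against.** The strongest reply is that the section 15 sentence is a safety provision. It covers both tasks and follows a remark about frustration and fatigue. A reader might infer that the assistant times or scores the search; the documents do not say so. A reader might also infer that everyone at the session knows the site. Section 6 implies this only for whoever places the coil, and section 20 leaves room for a second person. Section 22 mentions responding by button or by describing what is seen, which does not settle how the walking search is recorded. Capture might already be automatic. If so, one sentence would answer the recording part, but unscripted encouragement would remain.

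Second, object identification is a real control. A uniform change in encouragement between sites should affect both conditions, so a bias that mimics the full prediction must be specific to task and site. This narrows the concern. It does not remove it, because an observer who knows the hypothesis knows exactly that pattern.

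Third, masking is not always possible. If rTMS is given during the task, the person running it can see the coil, and so would a video. Video would also be a new, identifiable data type, whereas sections 6 and 8 limit collection to brain images and psychophysical data. These points stand and shape the fix.

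**Conclusion.** The point holds as a gap in the design of the walking experiment: recording method and recorder are unstated, the recorder is not masked, and contact during outcome collection is discretionary. The bias is possible, not demonstrated. A reader might go further and conclude that expectation alone would produce the predicted OPA result. The documents do not support that: they give no bias size and no scoring role for the assistant, and the identification control requires the bias to be selective.

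The rates of 7.0%, 13.1% and 23.6% are an illustration. They rest on assumed shifts of 0.1 to 0.3 SD, no true effect, n=19 and a two-sided paired test. This is a cheap improvement. It does not show that the experiment would give a wrong answer.

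**What to change.** Add to the protocol, for the walking experiment:

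- **Recording and script.** State the navigation measure and who records it. Record the start and end of each search with automatic time stamps. Use one fixed script for instructions, prompts and encouragement, identical for OPA and vertex runs and silent on the expected effect.
- **Separate roles where rTMS is given just before the task.** One of the at most two permitted staff places the coil. The other, absent during placement and not told the site, runs and records the search. If the section 20 limit is meant to cover both visits together, schedule the same two people accordingly.
- **Coded sites.** Label the sites A and B until any manual scoring is locked.

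If rTMS is given during the task, the person running it cannot be masked. Rely then on the time stamps, the fixed script and masked scoring of the time-stamped data.

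The cost is scheduling of existing staff and minor set-up. The time stamps and script need no additional person. Sample size, stimulation, visits and the assistant's safety presence are unaffected. Video is optional; it would mask scoring only, would leave in-room prompting untouched, and would require amending the data and confidentiality sections.
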